5.10 Treatment Compliance

For Visit 1, the morning dose will be administered in clinic by the subject under supervision from site personnel. For Visits 2, 3 and 4, the second dose will be administered by designated site personnel; all other doses will be administered by the subject.

In-between office visits, study compliance will be monitored by counting the number of used and unused vials dispensed and returned. Subjects will be instructed on instillation and storage of study treatment at the end of Visits 1, 2, 3, and 4, as well as provided written instructions. The subject's used and unused study treatment vials will be collected at each visit from Visit 2 up to and including Visit 5 to assess dosing compliance. Dosing compliance will be based off the used and unused vial count. If the subject is less than 80% or more than 125% compliant with dosing based on the expected number of used and unused vials, then the subject will be deemed non-compliant and a deviation should be recorded.

These guidelines will be used by the Investigator for determining the subject's necessary compliance for the study and for recording deviations from this compliance.

The study centers will keep an accurate accountability record that specifies the amount of study treatment dispensed to each subject, the amount of study treatment returned to the site, and the dates of each.

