6.10.2 Non-completing Subject

A non-completing subject is defined as one who exits the study by their own volition or at the discretion of the Investigator, the Medical Monitor, and/or an Aerie Safety Officer/designee. Any subject may decide to voluntarily withdraw from the study at any time without prejudice. If discontinuation of treatment is necessary, the Investigator will make every attempt to complete all subsequent safety assessments listed for the Early Termination Visit.

The subject may also be discontinued from the study for the following reasons:

- AEs (AEs including, in the opinion of the Investigator, clinically relevant laboratory abnormalities, and intercurrent diseases reported by the subject or observed by the Investigator with documentation on the CRF)
- Withdrawal of Consent
- Non-compliance (e.g., non-adherence to scheduled follow-up visits or use of study treatment)
- Lost to Follow-up
- Pregnancy
- Investigator Decision
- Protocol Deviation
- Death
- Other

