9.4.1 Intent-to-Treat (ITT) Population

The ITT population includes all randomized subjects. The primary efficacy analysis will be performed on the ITT population. Subjects in the ITT population will be analyzed as randomized.

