9.4.2 Per Protocol (PP) Population

The PP population includes subjects in the ITT population who do not have significant protocol deviations and who complete the trial through Day 28. Protocol deviations will be assessed prior to database lock and unmasking. The PP population will be analyzed using observed data only for efficacy variables. Subjects in the PP population will be analyzed as treated.

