5. STUDY SUBJECTS

5.1 Disposition of Subjects

Screen failures, subjects enrolled (i.e. subjects who entered the vehicle run-in period), subjects randomized, analysis populations, study completion, and withdrawal from the study will be summarized. The summary table will include screen failures, the number of subjects enrolled, the number of subjects randomized and included in the analysis populations by randomized treatment group for the ITT population and by actual treatment group for the PP and Safety populations. It will also include the numbers of subjects who completed and discontinued from the study. The reasons for subject discontinuation and test agent discontinuation will be summarized for the applicable subjects. Reasons for subject discontinuation will include adverse event (AE), withdrawal of consent, non-compliant, lost to follow-up, lack of efficacy, disallowed concurrent medication, investigator decision, protocol violation, death, and other.

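### Protocol 6.10.2 permits staff to take willing subjects out of the study for non-compliance or protocol deviation, so Day 28 ITT outcomes can be lost avoidably

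*Protocol*

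**What the plan says.** **Who may end participation, and from what.** Protocol 6.10.2 defines a non-completer as someone who leaves by their own choice or "at the discretion of the Investigator, the Medical Monitor, and/or an Aerie Safety Officer/designee". It continues: "The subject may also be discontinued from the study for the following reasons". The list includes "Non-compliance (e.g., non-adherence to scheduled follow-up visits or use of study treatment" and "Protocol Deviation". Withdrawal of consent and loss to follow-up are separate entries. No degree of deviation is specified, and Protocol 10.10 counts an out-of-window visit or a missed procedure as a deviation.

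**How the same events are treated elsewhere.**
- Protocol 5.10: a subject outside 80 to 125% of expected vial use, "then the subject will be deemed non-compliant and a deviation should be recorded".
- Protocol 10.10: sites are asked to remedy deviations quickly where they can.
- Protocol 9.4.1: "The ITT population includes all randomized subjects".
- Protocol 9.4.2: "The PP population includes subjects in the ITT population who do not have significant protocol deviations" and who complete through Day 28.

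**What is collected on exit.** Protocol 6.10.3 asks for every effort to hold a final visit after withdrawn consent or discontinuation for non-compliance; it does not name protocol deviation. The Early Termination list (Protocol 7.5) contains the symptom VAS but not the anesthetized Schirmer test, and the Schirmer rows in Protocol Appendix 4 and SAP Appendix 1 agree. SAP 8.3.2 places early-termination data at a scheduled visit only if they fall in that visit's window (Day 28 ± 2) and otherwise leaves them out.

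**Missing data.** Under Protocol 9.1.3 the primary analysis uses available data below 5% overall discontinuation and multiple imputation at 5% or more.

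**The concern.** The ITT comparison needs a Day 28 value from as many randomised subjects as possible, including those who adhered poorly or broke a rule. The plan already has a place for such subjects: they stay in ITT, and significant deviations take them out of PP. Section 6.10.2 opens a second route that ends their visits altogether. It can reach further than PP exclusion, because it has no threshold while PP exclusion requires a significant deviation.

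The events concerned may be linked to outcome. Poor adherence could follow poor tolerability of the active drops; use of a prohibited product such as artificial tears could follow lack of relief, perhaps more often on vehicle. An outcome that could have been observed would then become missing for reasons related to its value. Each such exit also counts toward the overall discontinuation rate that decides which analysis is primary.

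**Working it through.** **Step 1. The plan's own figures (Protocol 9.3).** Inputs: ODS-VAS difference 8.5, SD 19.0; Schirmer difference 1.4 mm, SD 3.15 mm; two-sided alpha 0.05; 90% power; 1:1:1 allocation. With n = 2(1.960 + 1.282)² × (SD/difference)² per group:
- ODS-VAS: n = 106; power at 108 is 0.908 (0.905 by noncentral t).
- Schirmer: n = 107; power at 108 is 0.904 (0.902 by noncentral t).
- Dropout: 108/0.90 = 120 per arm, 360 in total.

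The stated figures reproduce and 10% loss is budgeted. Power is not the issue.

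**Step 2. What a pre-Day 28 exit costs.**

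| Co-primary | Measured at Early Termination? | Usable at Day 28? |
|---|---|---|
| ODS-VAS | Yes (7.5) | Only if the visit falls on Days 26 to 30 |
| Anesthetized Schirmer | No (7.5, Appendix 4) | No |

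An exit after Visit 4 leaves both co-primaries intact and affects only Day 84.

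**Step 3. Possible size in an available-data analysis.** The documents give neither the number of such exits nor their link to outcome, so the share lost and the gap are assumptions. With loss in one arm only:

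shift in contrast = share lost × gap between retained and lost (in SD) × SD

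| Share of one arm lost | Gap 0.25 SD | Gap 1.0 SD | As % of 8.5 |
|---|---|---|---|
| 2% | 0.10 | 0.38 | 1.1 to 4.5% |
| 5% (6 of 120) | 0.24 | 0.95 | 2.8 to 11.2% |
| 10% (12 of 120) | 0.48 | 1.90 | 5.6 to 22.4% |

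For example, 0.05 × 1.0 × 19.0 = 0.95, and 0.95/8.5 = 11.2%. The percentages for Schirmer are nearly identical; at 5% and 1.0 SD, 0.05 × 3.15 = 0.158 mm of 1.4 mm. Under the null, 5% one-arm loss with a gap of 0.5 to 1.0 SD gives a two-sided type I error of about 0.054 to 0.067.

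**Step 4. Direction.** Two assumed cases point opposite ways.
- Six of 120 active subjects with no benefit are removed. The all-randomised effect is 8.5 × 0.95 = 8.075, while the retained subjects show 8.5: too large by 8.5/8.075 − 1 = 5.3%.
- Five per cent of vehicle subjects, each 15 mm worse than their arm mean, are removed. The vehicle mean shifts by 0.05 × 15/0.95 = 0.79, so the effect is 0.79/8.5 = 9.3% too small.

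**Step 5. Which analysis would apply.** Six exits are 6/360 = 1.7% of the trial and would not trigger imputation alone; 18/360 = 5% is the switch point. With 10% dropout planned, imputation is the likelier primary analysis. (At exactly 5%, SAP 8.3.1 prints both ≤ 5% and ≥ 5%; Protocol 9.1.3 has < 5% and ≥ 5%.)

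**The case against.** The strongest reply is that 6.10.2 grants a permission and reports no practice. It says a subject may be discontinued. No section makes a vial count, a missed visit or a prohibited product a trigger for removal, and 5.10 and 10.10 can coexist with a discretion that is rarely used. That stands: the claim is that outcomes can be lost, not that they are.

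Other points that stand in whole or part:
- **Timing.** After randomisation vials are counted at Visits 3, 4 and 5, so a vial-count removal can precede the Day 28 measures only at Visit 3 or at the start of Visit 4. Other deviations could surface at any time.
- **Non-attenders.** Someone who will not come has no Day 28 outcome to recover. The point concerns only willing, reachable subjects.
- **Mitigation.** The 6.10.3 final visit can rescue an in-window ODS-VAS, and multiple imputation is a partial remedy. Imputation details for the primary endpoints are not visible and may be redacted; nothing here rests on their absence.
- **Subject safety.** Some significant deviations carry added risk, and Visit 5 includes CAE exposure, so any new wording needs a safety exit.

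A reader might also infer that SAP 5.1 widens the removal powers, since its reasons end with "lack of efficacy, disallowed concurrent medication, investigator decision, protocol violation, death, and other". The document does not support that. The section is a reporting list, covers discontinuation of subject and of test agent separately, and authorises no exit.

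**Conclusion.** The point holds as a permissive gap. Section 6.10.2 allows willing subjects to be removed from the study for events that the ITT and PP definitions already handle. If that happens before Day 28, Schirmer is lost by procedure and ODS-VAS is usually lost through the visit window.

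The size and direction of any bias are unknown. At an assumed 5% loss in one arm and a gap of 0.25 to 1.0 SD, the available-data ODS contrast shifts by about 0.24 to 0.95 points, or 3 to 11% of 8.5. This would be smaller if fewer subjects are removed or if losses in the two arms offset, and it does not describe the result under multiple imputation.

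A reader might go further and conclude that the ITT result is biased in a known direction. The documents do not support that: they give no count of removals and no link to outcome, and the two plausible mechanisms act in opposite directions. Keeping consenting subjects to visits already scheduled is nevertheless cheap, and observing a value is better than modelling it.

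**What to change.** In Protocol 6.10.2, remove Non-compliance and Protocol Deviation as stand-alone reasons for discontinuation from the study, and add:

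> *Non-compliance with study treatment, use of a prohibited product, and other protocol deviations are recorded and may exclude the subject from the PP population; by themselves they do not end study participation, and are not grounds for exit under Investigator Decision or Other. The subject is asked to attend the remaining scheduled visits, including the Day 28 and Day 84 efficacy assessments, unless consent is withdrawn, the subject is lost to follow-up, or a safety reason applies.*

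Naming Investigator Decision and Other closes the route by which the same subject could still be exited under a different label.

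Leave two things as they are. The SAP 5.1 disposition categories should stay, so that exits that do occur remain visible under their real reason. The final-visit effort in 6.10.3 should stay for any subject who still leaves. Decisions about study treatment are not changed by this wording.

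Cost: a protocol wording change and the completion of scheduled visits for a few subjects. The ITT estimate may be slightly less favourable because poorly adherent subjects contribute observed values.

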6.10.3 Actions after Discontinuation

All subjects who discontinue study treatment due to a report of an AE must be followed and provided appropriate medical care until their signs and symptoms have remitted or stabilized or until clinically meaningful abnormal laboratory findings have returned to acceptable or pre-study limits.

For subjects who choose to withdraw consent or who are discontinued for non-compliance prior to completing the study, every possible effort should be made by the Investigator to assure there is a final visit that includes all examinations listed for the Early Termination Visit.

Clinical Study Protocol: AR-15512-CS201, Amendment 4

6.10.4 Discontinuation of the Entire Study

The entire study may be discontinued at a given site (by the Investigator or Aerie /Aerie representative) or at all sites by Aerie. Prompt, written notice of reasonable cause to all other relevant parties (Aerie or Investigator) is required. Prompt notice to the IRB and to regulatory authorities is also required.

6.10.5 Completed Study

The study is completed when the planned enrollment has been completed, and all the enrolled subjects have completed the study. An Aerie representative will be in communication with the investigational sites regarding enrollment.

7. STUDY ACTIVITIES

[figure not shown]
7.1 Screening Visit (Visit 1; Day -14 (+3*))

- Informed consent
- Inclusion and exclusion criteria
- Demographics
- Medical, ophthalmic, and surgical history
- Prior or concomitant medication review
- Adverse events
- Vital signs (heart rate and blood pressure)
- Urine pregnancy test (WOCBP only)
- Symptom Questionnaire (VAS) (Ocular Discomfort, Eye Dryness and Ocular Pain)
- SANDE Questionnaire (VAS)
- Ora Calibra Ocular Discomfort Scale (ODS)
- Best-corrected visual acuity
- Slit-lamp biomicroscopy
- At least 5 minute rest period
- Anesthetized Schirmer test

• A least 10 minute rest period

- CAE exposure
- Inclusion and exclusion criteria
- Symptom Questionnaire (VAS) (Ocular Discomfort, Eye Dryness and Ocular Pain)
- Ora Calibra Ocular Discomfort Scale (ODS)
- Slit-lamp biomicroscopy

- Review of qualification
- Hematology, chemistry, and urinalysis
- Intraocular pressure
- Dilated fundus exam
- Dispensing of the study treatment
- In office administration of study treatment
- AE review

^{*} Visit 1 should be scheduled between 11 and 14 days before Visit 2. If absolutely necessary, Visit 2 may be delayed up to 7 days (extending the run-in period to a maximum of 21 days).

7.2 Treatment Period

7.2.1 Visit 2 (Day 1; Baseline) Procedures

- Inclusion and exclusion criteria
- Collection of used and unused study treatment
- Concomitant medication review
- AE review
- Urine pregnancy test (WOCBP only)
- Symptom Questionnaire (VAS) (Ocular Discomfort, Eye Dryness and Ocular Pain)
- SANDE Questionnaire (VAS)
- Ora Calibra Ocular Discomfort Scale (ODS)
- Best-corrected visual acuity
- Slit-lamp biomicroscopy
- At least 5 minute rest period
- Anesthetized Schirmer test

• CAE exposure

- Inclusion and exclusion criteria
- Symptom Questionnaire (VAS) (Ocular Discomfort, Eye Dryness and Ocular Pain)
- Ora Calibra Ocular Discomfort Scale (ODS)
- Slit-lamp biomicroscopy

- Review of qualification
- Randomization
- Dispensing of Study Treatment
- At least 30 and up to 45 minute rest period
- Pre-drop non-anesthetized Schirmer test
- At least 15 and up to 20 minute rest period
- In office administration of study treatment

• AE review

7.2.2 Visit 3 (Day 14 ± 2) Procedures

- Collection of used and unused study treatment
- Concomitant medication review
- AE review
- Symptom Questionnaire (VAS) (Ocular Discomfort, Eye Dryness and Ocular Pain)

- SANDE Questionnaire (VAS)
- Ora Calibra Ocular Discomfort Scale (ODS)
- Best-corrected visual acuity
- Slit-lamp biomicroscopy
- At least 10 minute rest period

- Dispensing of Study treatment
- At least 15 and up to 20 minute rest period
- In office administration of study treatment
- AE review
- 7.3 Visit 4 (Day 28 ± 2) Procedures
 - Collection of used and unused study treatment
 - Concomitant medication review
 - AE review

- Symptom Questionnaire (VAS) (Ocular Discomfort, Eye Dryness and Ocular Pain)
- SANDE Questionnaire (VAS)
- Ora Calibra Ocular Discomfort Scale (ODS)
- Best-corrected visual acuity
- Slit-lamp biomicroscopy
- At least 5 minute rest period
- Anesthetized Schirmer test
- At least 10 minute rest period
- - CAE exposure (Selected Sites)
 - Symptom Questionnaire (VAS) (Ocular Discomfort, Eye Dryness and Ocular Pain)
 - Ora Calibra Ocular Discomfort Scale (ODS)
 - Slit-lamp biomicroscopy

• Dispensing of Study treatment

• In office administration of study treatment

• AE review

7.4 Visit 5 (Day 84 -5 / +2) Procedures

- Collection of used and unused study treatment
- Concomitant medication review
- AE review
- Urine Pregnancy test (WOCBP only)
- Symptom Questionnaire (VAS) (Ocular Discomfort, Eye Dryness and Ocular Pain)
- SANDE Questionnaire (VAS)
- Ora Calibra Ocular Discomfort Scale (ODS)
- Best-corrected visual acuity
- Slit-lamp biomicroscopy
- At least 5 minute rest period

• Anesthetized Schirmer test

- CAE exposure
- Symptom Questionnaire (VAS) (Ocular Discomfort, Eye Dryness and Ocular Pain)
- Ora Calibra Ocular Discomfort Scale (ODS)
- Best-corrected visual acuity
- Slit-lamp biomicroscopy

- Intraocular Pressure
- Dilated Fundus Exam
- AE review
- Study Exit

7.5 Early Termination Procedures

- Collection of used and unused study treatment
- Concomitant medication review

- AE review
- Pregnancy test (WOCBP only)
- Symptom Questionnaire (VAS) (Ocular Discomfort, Eye Dryness and Ocular Pain)
- SANDE Questionnaire (VAS)
- Ora Calibra Ocular Discomfort Scale (ODS)
- Best-corrected visual acuity
- Slit-lamp biomicroscopy
- Intraocular Pressure
- Dilated Fundus Exam
- Study Exit

7.6 Unscheduled Visits

An unscheduled visit may be any visit to the Investigator other than the specific visits specified in the protocol as possibly required for the subject's ophthalmic condition.

The investigator will perform all procedures necessary to evaluate the study participant at these visits and record any AEs in the CRF.

8. QUALITY CONTROL AND ASSURANCE

The progress of the study will be monitored by on-site, written, and telephone communications between personnel at the Investigator's site and the Sponsor and Study Monitor. The Investigator will allow the Sponsor or designee to inspect all CRFs; subject records (source documents); signed consent forms; records of study medication receipt, storage, preparation, and disposition; and regulatory files related to this study.

9. PLANNED STATISTICAL METHODS

9.1 Statistical Considerations

9.1.1 General Considerations

Quantitative variables will be summarized using number of subjects (n), mean, median, standard deviation, minimum and maximum. Qualitative variables will be summarized using counts and percentages.

All summaries will be presented by treatment group.

For the purpose of summarization, medical history, concurrent therapies, and AEs will be coded to MedDRA and WHO Drug dictionaries, as appropriate.

Baseline measures are defined as the last non-missing measure prior to the initiation of randomized study treatment. If a measure is taken both pre-CAE® and post-CAE®, baseline will be the time point matched value.

Change from baseline (CFB) will be calculated as visit – baseline; treatment comparisons will be calculated as AR-15512 – vehicle; and pre to post CAE comparisons will be calculated as post-CAE minus pre-CAE.

All primary and secondary analyses will be two-sided at a significance level of 0.05.

9.1.2 Unit of Analysis

[figure not shown]
Safety endpoints will be analyzed for both eyes. For efficacy endpoints, the unit of analysis will be the "study eye" as defined by the following:

The study subject must have one eye (the same eye) meeting all the inclusion criteria (Section 4.2) and none of the exclusion criteria (Section 4.3). Study subjects will be dosed in both eyes. If both eyes are eligible at the time of randomization, the study eye will be defined as the eye with the higher pre-CAE Ora Calibra ODS score at the Baseline visit. If both eyes qualify and have the same pre-CAE Ora Calibra ODS score, then study eye will be defined as the eye with the lower anesthetized Schirmer score at the Baseline visit. If both eyes still qualify, the right eye will be designated as the study eye.

9.1.3 Missing Data

The primary analysis will be completed with available data per subject from the intent-to-treat (ITT) population, assuming the overall study discontinuation rate is <5%. If the overall study discontinuation rate is $\ge5\%$ then the primary analysis will be based on the primary multiple imputation methodology and the available data analyses will become robustness analyses.

9.2 Hypotheses

The primary endpoints will be tested in a hierarchical fixed sequence in the following order.

 H_{01} : The difference between study eyes treated with AR-15512 (0.003%) and study eyes treated with vehicle, in the mean change from baseline (CFB) in pre-CAE ODS VAS at Day 28 = 0.

H₁₁: The difference between study eyes treated with AR-15512 (0.003%) and study eyes treated with vehicle, in the mean CFB in pre-CAE ODS VAS at Day $28 \neq 0$.

 H_{02} : The difference between study eyes treated with AR-15512 (0.003%) and study eyes treated with vehicle, in the mean CFB in pre-CAE anesthetized Schirmer score at Day 28 = 0.

 H_{12} : The difference between study eyes treated with AR-15512 (0.003%) and study eyes treated with vehicle, in the mean CFB in pre-CAE anesthetized Schirmer score at Day $28 \neq 0$.

 H_{03} : The difference between study eyes treated with AR-15512 (0.0014%) and study eyes treated with vehicle, in the mean CFB in pre-CAE ODS VAS at Day 28 = 0.

 H_{13} : The difference between study eyes treated with AR-15512 (0.0014%) and study eyes treated with vehicle, in the mean CFB in pre-CAE ODS VAS at Day $28 \neq 0$.

 H_{04} : The difference between study eyes treated with AR-15512 (0.0014%) and study eyes treated with vehicle, in the mean CFB in pre-CAE anesthetized Schirmer score at Day 28 = 0.

 H_{14} : The difference between study eyes treated with AR-15512 (0.0014%) and study eyes treated with vehicle, in the mean CFB in pre-CAE anesthetized Schirmer score at Day $28 \neq 0$.

Hierarchical fixed sequence testing will be employed to maintain the type I error rate. The primary analyses will first test the difference in the mean CFB in pre-CAE ODS VAS between treatments at Day 28, H_{01} . If the test of the difference is statistically significant at the two-sided alpha = 0.05 level in favor of AR-15512 (0.003%), then the trial will be considered a success; AR-15512 (0.003%) will be declared to be superior to vehicle in the mean CFB in pre-CAE ODS VAS at Day 28; and the difference in the mean CFB in pre-CAE anesthetized Schirmer score between treatments at Day 28, H_{02} , will be tested at the two-sided alpha = 0.05 level.

If in addition to a statistically significant test of the difference in the mean CFB in pre-CAE ODS VAS at Day 28 in favor of AR-15512 (0.003%), the test of the difference in the mean CFB in pre-CAE anesthetized Schirmer score at Day 28 is also statistically significant in favor of AR-15512 (0.003%), then AR-15512 (0.003%) will be declared to be superior to vehicle in both the mean CFB in pre-CAE ODS VAS and the mean CFB in pre-CAE anesthetized Schirmer at Day 28.

If H_{01} and H_{02} are both rejected in favor of AR-15512 (0.003%), then H_{03} and H_{04} will be tested in a similar hierarchical fashion using a two-sided alpha = 0.05.

If H₀₃ and H₀₄ are both rejected in favor of AR-15512 (0.0014%), then the secondary endpoints will be tested between AR-15512 0.003% and vehicle and between AR-15512

0.0014% and vehicle adjusting for multiplicity to maintain an overall two-sided alpha = 0.05 as detailed in the statistical analysis plan.

